2.4.5.2 Deaths

The incidence of death will be generated on the safety populations.

- Number (%) of patients who died by study period (on-treatment, treatment residual, and post-treatment).
- Death in non-randomized patients or randomized but not treated patients.
- TEAE leading to death (death as an outcome on the AE CRF page as reported by the Investigator) by primary SOC and PT, showing number (%) of patients sorted by internationally agreed order of SOC and decreasing frequency of PT within a SOC in the Sarilumab 200mg q2w treatment group.

Listings will be provided for all deaths with flags indicating during treatment or post-treatment status.

2.4.5.3 Analyses of laboratory variables

The summary statistics (including number, mean, median, SD, minimum and maximum) of all laboratory variables (central laboratory values and changes from baseline) will be calculated for each visit or study assessment (baseline, each post baseline time point, endpoint) by treatment group. This section will be organized by biological function as specified in [Section 2.1.4.3](#).

In addition, for all laboratory parameters, the mean value and mean change from baseline at each scheduled visit during the treatment period will be plotted by treatment group.

The incidence of PCSAs (list provided in [Appendix C](#)) at any time during TEAE period will be summarized by biological function and treatment group whatever the baseline level and/or according to the following baseline status categories:

- Normal/missing
- Abnormal according to PCSA criterion or criteria

For lipids, the National Cholesterol Education Program Adult Treatment Panel III (NCEP ATP III) classification will be used for the baseline.

The incidence of abnormal laboratory values at any time during the TEAE period will be summarized in shift tables by biological function and treatment group whatever the baseline level and/or according to the following baseline status categories:

- Normal/Missing
- Abnormal high according to the normal range
- Abnormal low according to the normal range

Time to onset of the initial LDL-C elevation (≥ 4.1 mmol/L, ≥ 4.9 mmol/L), time to onset of the initial total cholesterol elevation (≥ 6.2 mmol/L), time to onset of the initial Grade 3 or Grade 4 neutropenia (neutrophil count < 1.0 Giga/L), time to onset of the initial platelet count < 100 Giga/L, time to onset of the initial lymphocyte count < 1.0 Giga/L, time to onset of the initial ALT elevation (> 3 x ULN, > 5 x ULN), time to onset of the initial AST elevation (> 3 x ULN, > 5 x ULN), and time to onset of initial total bilirubin > 2 x ULN will be analyzed using Kaplan-Meier estimates, using the midpoint of the time interval between the first assessment showing the elevation and the previous assessment, presented by treatment group.

Listings will be provided with flags indicating the out of range values as well as the PCSA values.

Neutrophils

The incidence of neutropenia by maximal grade (lowest absolute neutrophil count reported during the TEAE period) will be summarized. The 4 grades are defined as below:

- Grade 1: ≥ 1.5 Giga/L-LLN.
- Grade 2: ≥ 1.0 Giga/L- < 1.5 Giga/L.
- Grade 3: ≥ 0.5 Giga/L- < 1.0 Giga/L.
- Grade 4: < 0.5 Giga/L.

Thrombocytopenia

The incidence of thrombocytopenia by maximal grade (lowest platelet count reported during the TEAE period) as defined below will be summarized.

- ≥ 75 Giga/L-100 Giga/L.
- ≥ 50 Giga/L- < 75 Giga/L.
- ≥ 25 Giga/L- < 50 Giga/L.
- < 25 Giga/L.

Hepatic disorders

The liver function tests, namely AST, ALT, ALP, and total bilirubin are used to assess possible drug-induced liver toxicity. The proportion of patients with PCSA values at any post-baseline visit by baseline status will be displayed by treatment group for each parameter. The proportion of patients with PCSA values at any post baseline visit may be displayed by duration of exposure for each treatment group.

A graph of distribution of peak values of ALT versus peak values of total bilirubin will also be presented. Note that the ALT and total bilirubin values are presented on a logarithmic scale. The graph will be divided into 4 quadrants with a vertical line corresponding to 3x ULN for ALT and a horizontal line corresponding to 2x ULN for total bilirubin.

2.4.5.4 Analyses of vital sign variables

The summary statistics (including number, mean, median, SD, minimum, and maximum) of all vital signs variables (vital signs values and changes from baseline) will be calculated for each visit or study assessment (baseline, each post baseline time point, endpoint) by treatment group.

The incidence of PCSAs at any time during the TEAE period will be summarized by treatment group whatever the baseline level and/or according to the following baseline status categories:

- Normal/Missing
- Abnormal according to PCSA criterion or criteria

Listings will be provided with flags indicating the PCSA values.

2.4.6 Analyses of pharmacokinetic variables

All the PK analyses will be performed using the PK populations including only the sarilumab treated patients.

Serum concentrations of functional sarilumab (both pre-dose and post-dose) will be summarized using descriptive statistics (including number, arithmetic and geometric means, SD, standard error of the mean, coefficient of variation, minimum, median, and maximum) for each visit. The pre-dose samples will be considered non-eligible for these analyses if the previous dosing time is <11 days or >17 days before the sampling time for every other week regimens. Concentrations below the lower limit of quantification (LLOQ) will be set to zero for samples at baseline (i.e., pre-dose at Week 0). Other post-treatment concentrations below LLOQ will be replaced by LLOQ/2. In addition, serum concentrations of functional sarilumab will be summarized using descriptive statistics mentioned above by immunogenicity status for each visit.

2.4.7 Analyses of quality of life variables

Descriptive statistics including number of subjects, mean, median, SD, minimum, maximum will be provided by treatment groups for the value and change from baseline at each visit (baseline, Week 12, Week 24 and Week 52) for the 2 summary measures of SF-36 (physical component summary score and mental component summary score) and the 8 domains, the quantitative variables of EQ-5D-3L (visual analog scale and single index utility), FACIT-Fatigue, HAQ-DI (standardized score, pain score and patient global assessment) and MD-VAS. Change from baseline at each visit will also be plotted by treatment groups.

The change from baseline at Week 52 for the above measures will be analyzed with mixed model repeated measures (MMRM) approach. The repeated-measures analysis will be based on the

restricted maximum likelihood method assuming an unstructured covariance structure to model the within-subject errors. The model, including treatment, visit, and treatment -by -visit interaction, baseline and baseline -by -visit interaction as covariates, will be used to test the difference of least square means (LS means) between treatment groups in the change from baseline in each variable. Descriptive statistics including number of subjects, mean, standard error and LS means will be provided. In addition, difference in LS means between treatment groups, the corresponding 95% CI and the p-value will be provided.

2.4.8 Analysis of immunogenicity endpoints

The following summary will be provided separately for ADA positive patients, ADA negative patients, patients with persistent ADA response, and patients with transient ADA responses.

ADA prevalence and titer

The following summary will be provided based on the ADA populations:

- Number (%) of patients with an ADA positive sample at baseline:
 - Number (%) of neutralizing antibody.
 - Number (%) of non-neutralizing antibody.
 - The summary statistics (including number, median, Q1, Q3, minimum and maximum) of the titer for the baseline ADA positive patients.
- Number (%) of patients with an ADA negative sample at baseline.

ADA incidence and titer

The following summary will be provided based on the ADA populations during TEAE period:

- Number (%) of ADA-negative patients.
- Number (%) of ADA-positive patients:
 - Number (%) of patients with neutralizing antibody.
 - Number (%) of patients with non-neutralizing antibody.
 - The summary statistics (including number, median, Q1, Q3, minimum, and maximum) of the peak post-baseline titer for all ADA-positive patients.
- Number (%) of treatment-emergent ADA-positive patients:
 - The summary statistics (including number, median, Q1, Q3, minimum, and maximum) of the peak post-baseline titer for treatment-emergent ADA-positive patients.
 - Number (%) of transient treatment-emergent ADA-positive patients:
 - Number (%) of patients with neutralizing antibody.
 - Number (%) of patients with non-neutralizing antibody.

- Number (%) of persistent treatment-emergent ADA positive patients:
 - Number (%) of patients with neutralizing antibody.
 - Number (%) of patients with non-neutralizing antibody.
- Number (%) of persistent treatment-emergent ADA positive patients because last sample was positive.
- Number (%) of treatment-boosted ADA positive patients:
 - Number (%) of patients with neutralizing antibody.
 - Number (%) of patients with non-neutralizing antibody.
 - The summary statistics (including number, median, Q1, Q3, minimum, and maximum) of the peak post-baseline titer for all treatment-boosted ADA-positive patients.

In addition, number (%) of patients with ADA positive or negative response at each visit will be summarized by treatment group.

ADA and PK

By visit descriptive summary of functional sarilumab concentrations in serum will be provided by ADA patient classifications (positive or negative) for the sarilumab treatment groups.

ADA and clinical safety

The safety assessment will focus on the following events:

- Hypersensitivity (standardized MedDRA query (SMQ): Hypersensitivity [Narrow]).
- Anaphylaxis (SMQ: Anaphylaxis [Narrow]).
- Injection-site reactions (HLT: Injection site reactions).
- TEAEs leading to permanent treatment discontinuations.

Number (%) of patients with these events will be summarized by ADA patient classifications (positive or negative) for the sarilumab treatment group. The relationship between the timing and the titer of the positive ADA and events may also be explored as necessary.

ADA and clinical efficacy

The following efficacy endpoints will be analyzed by ADA patient classifications (positive or negative; persistent, transient; neutralizing, non-neutralizing):

- Proportion of patients achieving sustained remission at Week 52
- Number (%) of patients with lack of efficacy.

Lack of efficacy is defined as permanent treatment discontinuation due to lack of efficacy.

2.4.9 DNA/RNA

The DNA test is optional and patients need to sign a separate informed consent for DNA testing. Exploratory analysis of DNA/RNA will be addressed in a separate document by a separate biomarker analysis group.

2.5 DATA HANDLING CONVENTIONS

2.5.1 General conventions

The following formulas will be used for computations of parameters.

Demographic formulas:

BMI is calculated as follows:

$$\text{BMI} = \text{Weight in kg}/(\text{height}^2 \text{ in meters}).$$

2.5.2 Data handling conventions for secondary efficacy variables

GTI

General Considerations

For vital signs and laboratory data used together with the GTI CRF to derive the scoring the scheduled measurements at the time of the visit should generally be used, but if any of these are missing they can be replaced by the last available measurement in the corresponding time window for that parameter.

GTI missing domains

The missing lab measurement for any GTI domain at a visit will be imputed by last observation carried forward (LOCF) method, and missing medication information for Glucose, Blood Pressure and Hyperlipidemia domains will be imputed as 'no change' in order to calculate the composite and cumulative GTI scores. For patients who discontinued study treatment prematurely (prior to Week 52), domain scores after treatment discontinuation visit will be considered as 'no change' for the calculation of cumulative GTI scores at Week 52. No imputation will be performed for cumulative GTI scores at Week 52 for patients with no post-randomization measurements (i.e. will not carry forward from baseline).

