#### **10.4.4 Handling of patients after permanent treatment discontinuation**

Every effort should be made to maintain patients in the study after permanent study treatment discontinuation. Patients should be followed up according to the study procedures as specified in this protocol up to the scheduled date of study completion, or up to recovery or stabilization of any AE to be followed-up as specified in this protocol, whichever comes last. The scientific value of the complete collection of data will be explained to patients, and site personnel will receive training regarding strategies for patient retention, and access to tools to assist with this during the study.

If a patient prematurely and permanently discontinues study treatment, a premature end of treatment (EOT) visit (see [Section 10.4.2](#)) should be scheduled at the time of treatment discontinuation, if possible. If not possible, the EOT should be scheduled as soon as possible after treatment discontinuation. The IRT should be notified of EOT. Of note, during this premature EOT visit, the bone density test does not need to be performed if it has been less than 6 months since the bone density test associated with the baseline visit.

Following the premature EOT visit, the remaining visits will be performed as scheduled. All efforts should be made to follow the patients for safety for at least 6 weeks after last dose of SC IMP and for primary endpoint and key secondary endpoints through the remainder of the study visits up to Week 52 after premature EOT.

All cases of permanent treatment discontinuation should be recorded by the Investigator in the appropriate pages of the CRF when considered as confirmed. Details recording the specific reasons for discontinuation should be collected.

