For the management of pre-defined laboratory abnormalities, investigators may temporarily hold the study drug (sarilumab or its matching placebo) and/or permanently reduce the dose of sarilumab (or its matching placebo) to 150 mg q2w in a continuous blinded manner.

There will be a post treatment follow-up visit 6 weeks after the end of treatment visit. All patients who prematurely and permanently discontinue study treatment will be asked to return to the site for study assessments as per protocol until end of study (EOS) evaluation. The last patient last visit will occur when the last patient has completed the 6-week follow up period (EOS). The end of the clinical trial is defined as the last patient's last visit.

Approximately 280 patients are planned to be randomized into 2 treatment groups of 140 patients per group.

Study discontinuation plan

As mentioned in [Section 1](#), due to the protracted recruitment timeline and internal portfolio reprioritization, Sanofi decided to terminate the EFC15160 study in July 2020. All randomized patients continued to complete the study per protocol, and the last patient last visit (EOS) was achieved on May 19, 2021.

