The Composite GTI consists of nine domains (body mass index (BMI), glucose tolerance, blood pressure, Hyperlipidemia, Bone Health (BMD), steroid myopathy, Skin steroid-related Toxicity, Neuropsychiatric – steroid related symptoms and infection) on common steroid-related adverse events anticipated to occur in $\geq 5\%$ of patients treated in a clinical trial involving glucocorticoids. The Specific List consists of 23 items (11 domains) that are mainly less common but serious adverse effects, serving as a complementary tool to the Composite GTI to ensure that all important elements of glucocorticoid toxicity were captured.

The domains of the Composite GTI and the specific list of the GTI will be assessed at baseline, Week 12, Week 24, Week 40 and Week 52, except for bone density (BMD) which will be assessed at Baseline and Week 52 only.

For patients who withdraw from the study prior to Week 24, BMD will not be measured at the EOT visit as no substantial changes are expected within 6 months of treatment. As a result, missing BMD score will be imputed as 'no change'. The BMD measured at the end of treatment (EOT) visit will be included in the definition of cumulative GTI scores (i.e., CWS and AIS as defined below) at Week 52 regardless when the EOT visit occurred.

Scoring of the Glucocorticoid Toxicity Index (GTI)

Domain-specific score for each patient at a visit is defined as the weight assigned based on the change in severity level as described for each domain in [Table 2](#).

Composite GTI score for each patient at a visit is the sum of 9 domain-specific scores at each visit.

Cumulative GTI score is the sum of composite GTI score across visits. Two cumulative GTI scores, CWS and AIS, will be defined.

- **Cumulative worsening score (CWS)**

CWS is designed to assess cumulative GC toxicity, regardless of whether the toxicity has lasting effects or is transient. New toxicities that occur are added, but toxicities that appear to resolve on follow-up are not removed. Thus, the CWS serves as a lasting record of GC toxicity observed and can only increase or remain the same over time.

CWS will be lower in the treatment arm compared to the placebo arm at the end of trial, if the treatment is effective at decreasing GC toxicity over time.

- **Aggregate improvement score (AIS)**

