Patients are anticipated to have some GC toxicity at baseline, the AIS would be important in establishing that the new therapy is effective at diminishing any baseline GC toxicity over time. With the AIS, toxicities can be removed if improvement occurs, and added if worsening occurs.

AIS decrease over time means that the treatment is effective in decreasing GC toxicity level, compared to placebo which may show fluctuation of CIS over time. Negative score reflects that toxicities present at baseline (or occurring during the trial) resolved over the treatment period.

The steps to calculate the CWS and AIS at Week 52 are described below.

Step 1: Calculate domain-specific worsening score (for computing CWS in Step 2) and improvement score (for computing AIS in Step 2) at each visit.

For Domains without sub-items (Body Weight, Glucose Metabolism, Blood Pressure, Lipid Metabolism, Bone Health and Steroid Myopathy),

- a) For worsening score, only consider positive domain-specific score at each visit. For domain with a negative domain-specific score, the worsening score will be 0.

- b) For improvement score, all domain-specific scores (could be positive or negative) at each visit will be considered.

The Skin and Neuropsychiatric domains both have sub-items. For the Skin domain, these are Acneiform Rash, Easy Bruising, Hirsutism, Atrophy/Striae, and Erosions/tears/ulcerations. For the Neuropsychiatric domain, these are Insomnia, Depression, Mania, and Cognitive Impairment.

- a) For worsening score, only the item with the highest weight is scored for any GTI interval (typically three months) with the CWS. As an example, if neither insomnia nor depression were present at the baseline visit but there is now mild Insomnia and moderate depression present at follow-up, then only the moderate depression is scored (+63 points).
- b) For improvement score, improvement as well as worsening can be recorded. Because it is conceivable that one item might improve while another worsens, the item of greatest improvement (highest absolute weight) and the item of greatest worsening (highest weight) are recorded for given GTI interval.

For Infection Domain, the worsening score and improvement score handle the scoring of infections differently, because the CWS and AIS reflect reciprocal measures of GC toxicity.

- a) For worsening score, the most severe infection in every GTI interval is scored.

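### The SAP sets GTI domain scores after treatment discontinuation to no change in the cumulative scores, whether or not they were observed, which biases the CWS towards the arm with more discontinuation

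*SAP*

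**What the plan says.** SAP 2.5.2, under "GTI missing domains", has three relevant steps. Missing laboratory values for a domain are carried forward, and missing medication information is taken as no change. Then: "For patients who discontinued study treatment prematurely (prior to Week 52), domain scores after treatment discontinuation visit will be considered as" no change for the cumulative GTI scores at Week 52. Last, no cumulative score is imputed for patients without any post-randomization measurement. The first step is expressly about missing data; the trigger in the second is treatment discontinuation alone.

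Protocol 10.4.4 says of patients who stop: "Following the premature EOT visit, the remaining visits will be performed as scheduled". It adds that all efforts should be made to follow them "for primary endpoint and key secondary endpoints through the remainder of the study visits up to Week 52 after premature EOT". SAP 1.1 agrees: "All patients who prematurely and permanently discontinue study treatment will be asked to return to the site for study assessments as per protocol". SAP 2.1.3.2 schedules the GTI at baseline and Weeks 12, 24, 40 and 52, with bone density (BMD) at baseline and Week 52 only.

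SAP 2.1.3.2 builds each cumulative score by summing the four post-baseline visit scores. On the CWS it says: "Thus, the CWS serves as a lasting record of GC toxicity observed and can only increase or remain the same over time". On the AIS: "With the AIS, toxicities can be removed if improvement occurs, and added if worsening occurs". SAP 2.4.4.2 analyses both by ANCOVA with a p-value, and gives odds ratios for CWS = 0 (not worsening) against CWS > 0, and for AIS < 0 (improved) against AIS ≥ 0.

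**The concern.** Reducing glucocorticoid toxicity is a stated secondary objective, and the CWS and AIS are its modelled analyses. If a patient stops treatment, attends Weeks 24, 40 and 52 and develops toxicity there, the rule replaces that toxicity with zero in both scores. Under Protocol 10.4.2, permanently stopping the injections means stopping the oral taper too, so any steroid taken later is outside the protocol taper and its toxicity is what the rule removes. The cumulative steroid dose endpoint would not reveal it, because SAP 2.4.4.2 counts actual dose only up to the end of treatment.

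The handling also contrasts with the primary endpoint. Under SAP 2.1.3.1, permanent withdrawal from study treatment makes the patient a failure on sustained remission. In the CWS, the same event earns the most favourable value available at every later visit.

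**Working it through.** The plan has no figure that depends on this rule, so there is nothing to reproduce first. The SAP's power table concerns the primary endpoint only.

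**Direction for the CWS.** At each visit a domain contributes its weight if positive and 0 otherwise (SAP 2.1.3.2, Step 1). Every visit score is therefore at least 0, and setting it to 0 can lower the CWS or leave it unchanged, never raise it. The largest amount one overwritten visit can remove, from the maximum weights in SAP Table 2 without BMD, is 36 + 44 + 44 + 30 + 63 + 26 + 74 + 93 = 410 points. A patient who stops at Week 12 loses three of the four visits: 75% of the CWS if worsening accrues evenly, and all of it if the worsening comes later.

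**Size for the CWS.** Suppose true worsening is the same in both arms, with mean *m* per visit, and a patient who stops has *k* visits zeroed on average. If the arms differ by *d* in the proportion stopping, then

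spurious CWS difference = *d* × *k* × *m*.

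If worsening accrues evenly, the bias relative to the mean CWS is *d* × *k*/4. The documents give none of *d*, *k*, *m* or the SD; all values below are assumptions. The false-positive rate is for a two-sided 5% comparison of means with 59 per arm, SE = SD × √(2/59), which is 9.2 for SD 50 and 18.4 for SD 100, without covariate adjustment.

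| Gap *d* | Visits zeroed *k* | Points per visit *m* | CWS difference | False positives, SD 50 | False positives, SD 100 |
|---|---|---|---|---|---|
| 5 points | 1 | 10 | 0.5 | 5.0% | 5.0% |
| 10 points | 2 | 20 | 4.0 | 7.2% | 5.5% |
| 20 points | 2 | 20 | 8.0 | 14.0% | 7.2% |
| 20 points | 3 | 40 | 24.0 | 74.1% | 25.6% |

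One further case: 30% v 15% stopping, two visits zeroed and 26 points per visit gives 0.15 × 2 × 26 = 7.8 points. Against a mean CWS of 4 × 26 = 104 that is 7.5%, which equals 0.15 × 2/4.

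**Direction for the AIS.** Visit scores can have either sign. With 20 percentage points more stopping in one arm and two visits zeroed, that arm's mean shifts by −0.20 × 2 × *a*, where *a* is the mean of the discarded visit scores: −8 (looks better) if *a* = +20, 0 if *a* = 0, and +8 (looks worse) if *a* = −20.

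**Categories.** A patient who stops by Week 12 with no change up to then is fixed at CWS = 0 and AIS = 0. That counts as not worsening on one scale (favourable) and not improved on the other (unfavourable), whatever is observed later.

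**The case against.** The strongest defence is the heading. The rule stands among conventions for missing domains, so it may have been meant only for visits that did not take place, in which case nothing observed is overwritten. That reading is available, but the sentence does not say it, and its neighbour does state a missingness condition. Even on this reading zero remains the most favourable CWS value, so the built-in direction stays for the imputed visits.

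Several stronger conclusions are tempting, and the documents do not support them:

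- *The arm with more discontinuation looks safer on the GTI as a whole.* This holds for the CWS only. The AIS also loses observed improvement.
- *All later toxicity disappears from the report.* The rule names only the cumulative scores. The by-visit summaries and Specific List counts (SAP 2.4.4.2) are outside it, and BMD at the EOT visit is kept whenever that visit occurred (SAP 2.1.3.2).
- *The toxicity of rescue steroids is discarded.* Rescued patients should normally continue the injections (Protocol 8.2). If study treatment means the SC product, they have not discontinued and their scores are kept. The rule does not define the term.
- *The post-discontinuation data exist.* They are planned. Follow-up is on an all-efforts basis, key secondary endpoint is undefined, Protocol 9.8 calls the GTI one of the other efficacy endpoints, and patients may withdraw.
- *The ITT principle is broken.* SAP 2.3.1.1 defines ITT by who is analysed and in which arm, and patients who stop remain in the ANCOVA. The gap is an unstated strategy for data after discontinuation.
- *The rule favours sarilumab.* Discontinuation rates by arm are not given.

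**Conclusion.** The concern stands in this limited form. Read as written, the rule overwrites scheduled and possibly observed GTI scores in the CWS and AIS. For the CWS the direction is certain: the ANCOVA and the not-worsening comparison both lean towards the arm with more discontinuation. For the AIS the direction is unknown.

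The size cannot be fixed from the documents. Over the assumed range it runs from negligible (0.5 points) to large (24 points), and a middle case of 4 points barely moves the false-positive rate. The bias from this rule is zero if the arms lose equal amounts of worsening to zeroed visits.

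SAP 2.4.4.4 names only cumulative steroid dose after the primary endpoint, so neither the primary result nor that test is affected. What is at risk is the conclusion on glucocorticoid toxicity. The change should be made because the direction is built in and the remedy is cheap, not because a large error has been shown.

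**What to change.** In SAP 2.5.2:

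1. Use observed domain scores at all scheduled visits in the CWS and AIS, whatever the treatment status, and state that this is the strategy for data after discontinuation.
2. Impute only post-discontinuation scores that are truly missing, by multiple imputation. Do not extend LOCF to them. If scores are changes since the last visit, a carried-forward value gives no change, which is the present rule again; if they are changes from baseline, LOCF adds the same toxicity once more at each later visit.
3. Say whether study treatment in this rule means the SC product, the oral product or both.
4. Keep the no-change rule as a sensitivity analysis only.
5. Report by arm the number of post-discontinuation GTI visits that were due and the number observed, so that readers can judge how much rests on imputation.

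The cost is SAP wording and a little extra programming. No assessment beyond the existing schedule is needed.
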